6.2.2 Dosing Delay for the Peptide Vaccines (K27M/TT emulsified in Montanide ISA-51)

Possible adverse events by Montanide ISA-51-based peptide vaccines are summarized in Section 6.1.1.3. The toxicity profile may partially overlap with that of poly-ICLC, though the attribution to either or both of these agents may be apparent if the reactions/events are localized to the administration site or follow specific timings after the administration (e.g. fever after poly-ICLC administration). In circumstances where poly-ICLC administration is suspended, if the event is not attributable to the peptides/Montanide ISA-51 vaccine, vaccine administration should continue on schedule. In circumstances where assessment of an adverse event is limited, such as by intercurrent illness, or when laboratory studies are required to assess for other causes of toxicity, the vaccine schedule may be interrupted for up to 6 weeks. If vaccine administration is delayed by longer than 6 weeks due to an adverse event other than for pseudo-tumor progression, regardless of attribution, treatment must be discontinued.

6.2.3 Dose modification for Nivolumab

See Appendix I for management algorithms.

6.3 Regimen Limiting Toxicity (RLT)

Each patient receiving K27M/TT peptide vaccination and poly-ICLC or K27M/TT peptide vaccination and poly-ICLC in combination with nivolumab will be evaluable for safety. The safety parameters include all laboratory tests and hematological abnormalities, physical findings, and spontaneous reports of adverse events reported to the investigator by patients.

RLT includes any of the following events that occur during the first 8 vaccine doses (the entirety of the time from the 1st vaccine administration through the 8th vaccine administration) and up to 30 days after the 8th vaccine administration and are considered either possibly, probably, or definitely to the vaccine:

- Any grade 2 or greater autoimmune reaction.
- Any grade 3 or greater hematologic or non-hematologic toxicity with the exception of lymphopenia.
- Any life-threatening event.
- Any other unexpected Grade 2 or greater neurological deficit, which is possibly, probably, or definitely related to the vaccine therapy that does not respond within 21 days trial of 0.3mg/kg day dexamethasone or equivalent (max 12mg/day) or Avastin equivalent (10mg/kg every 2 weeks for a maximum of 3 doses)

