3.5 Study Timeline

This study aims to enroll 19 HLA-A2 (02:01)⁺ children with H3.3K27M positive DIPG (Stratum A), 10 HLA-A2 (02:01)⁺ children with H3.3K27M positive midline gliomas other than DIPG, including spinal cord tumors (Stratum B) and 20 HLA-A2 (02:01)⁺ children with H3.3K27M positive DIPG or midline gliomas other than DIPG, excluding primary spinal cord tumors (Stratum C). H3.3K27M status needs to be confirmed in a CLIA or equivalent approved laboratory. Eligible patients with positive H3.3K27M need to also test positive for HLA A*02:01in a CLIA or equivalent approved laboratory.¹⁴ We will enroll into the 3 strata separately, and the first 3 patients in each stratum will be observed for RLTs for at least 6 weeks before the next set of patients are enrolled in that stratum. We will enroll subjects onto stratum C once we have met total accrual onto strata A and B. See Section 9.3 for further information.

Based on our accrual into this trial we anticipate to enroll an average of 1.8 subjects per month. We anticipate that enrollment for strata A, B, and C will be similar and therefore we anticipate that enrollment into the K27M glioma strata will be completed in about two years for each stratum.

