Strata A & B: If the subject demonstrates stable to improved disease to the vaccine therapy and tolerates the therapy well (defined as not having any regimen related toxicities RLT; see below), patients may receive additional vaccinations every 6 weeks after the 8th dose starting at Week 30 for a total of 96 weeks (approximately 2 years).

Stratum C: On the same day (+/- 3 days) as the vaccination with K27M/TT and poly-ICLC, stratum C patients will receive nivolumab 4.5 mg/kg IV, every 3 weeks, through week 21 of the study procedures. If the subject demonstrates stable to improved disease to the vaccine therapy and nivolumab combination therapy and tolerates the therapy well (defined as not having any regimen related toxicities RLT; see below), stratum C patients may continue to receive nivolumab every 3 weeks after the 8th dose for a total of 96 weeks (approximately 2 years). Patients may receive additional vaccination with K27M/TT and poly-ICLC combined with nivolumab every 6 weeks after the 8th dose and will resume combination therapy, starting at Week 27, for a total of 96 weeks (approximately 2 years).

Because the peptide vaccine is sequestered locally and the immune response occurs primarily locally, the dose of the vaccine does not need to be scaled up proportionately to weight or body surface area; however, nivolumab will be based on the weight measured within 7 days prior to each infusion. With regard to the dose of poly-ICLC we will use a fixed amount of 30 micrograms/kg, which was used previously and demonstrated good tolerability with only grade 1-2 adverse events (injection site reactions, flu like and GI symptoms)¹⁴. The K27M/TT specific peptide will be emulsified in the adjuvant Montanide ISA-51, which consists of a mineral oil base, which has demonstrated to be well tolerated in previous studies¹⁴.

- 6.1 Dosage and Administration
- 6.1.1 Dosage
- 6.1.1.2 Poly-ICLC

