- 18. If a patient has evidence of progressive disease and is undergoing tumor tissue resection as part of standard of care, a sample should be sent to UCSF for further analysis to assess antigen loss and immune cell infiltration. Please see Section 9.2.2 for further details. Please refer to PNOC SharePoint member website for shipping information.

Table 6.2 Schedule of Study Procedures and Assessments (Stratum C)

Study Day/Visit	Eligibility (-14 days) ¹	Day 1 on Weeks 0, 3, 6, 9, 12, 15, 18, 21, 24, 27, 33, 39, 45, 51, 57, 63, 69, 75, 81, 87, 93, and 96 (-3 days) ²	End of Treatment Visit (-14 days) ³	30 Day Toxicity Check (+7 days) ⁴	Follow-Up⁵
Clinical procedures					
HLA typing	X6				
H3.3K27M mutation status	X6				
Consent Form	x				
Physical Exam ⁷		x	Х		
Vital Signs		X	Х		
Pulse oximetry	Х	Х	Х		
Medical History ⁸	Х				
Performance Status	x	Х	Х		
Adverse Event assessment ⁹	x	Х	Х	х	x
Concomitant Medications	x	х	х	х	
Drug administration • Vaccine ¹⁰ • Poly-ICLC ¹¹ • Nivolumab ²⁰ (every 3 weeks through 96 week study)		x	х		
Evaluation of clinical response			х		
Survival ⁵					x
Laboratory procedures					
CBC w/ Diff + plts	Х	X ¹²	X ¹²		
Blood Chemistry	X ¹³	X ^{12,13}	X ^{12,13}		
Pregnancy test ¹⁴	x	x	х		
Urinalysis	X	X	X		
CPK & cardiac troponins		x	х		
Imaging/cardiology procedures					
ECG ¹⁵		Х	х		

ECHO ¹⁵		Х	х	
Brain MRI/Spine MRI	X ¹⁶	X ¹⁶		
Quality of Life Assessments				
QOL Assessments(see Appendix H for specific timepoints)	х	Х	х	х
Specimen Collection				
Immune monitoring tests ¹⁷		Х		
Blood for ctDNA 18		Х		
Tumor Tissue Collection ¹⁹	х			

- 1. Eligibility tests and procedures must be performed within 14 days prior to enrollment. Consent to study therapy must be signed. H3.3K27M sequencing and HLA typing may be done prior to 14 days within enrollment.
- 2. If the subject demonstrates no evidence of disease progression and tolerates the therapy well (defined as not having any regimen related toxicities (RLT); see Section 6.3) after the 8th dose (Week 21), patients may continue to receive nivolumab every 3 weeks after the 8th dose for a total of 96 weeks. Patients may receive additional vaccination with K27M/TT and poly-ICLC combined with nivolumab every 6 weeks after the 8th dose (starting at Week 27) for a total of 96 weeks.

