10.1.4 Design

We will enroll into the 3 strata separately: Stratum A consists of HLA-A02:01⁺ positive newly diagnosed patients with H3.3K27M positive DIPG, stratum B consists of other HLA-A02:01⁺ positive newly diagnosed patients with H3.3K27M positive gliomas that are not classified as DIPG, including spinal cord tumors and stratum C consists of subjects with HLA-A02:01⁺ H3.3K27M positive DIPG or other HLA-A02:01⁺ H3.3K27M positive midline gliomas, excluding primary spinal cord tumors. The separation of strata A and B is based on anticipation that toxicity of the vaccine and Poly-ICLC could be significantly different based on the primary tumor location. Toxicities resulting from pseudoprogression or local reaction (such as edema or inflammation) may manifest differently when tumors are located within the brainstem (as in DIPG) versus outside the brainstem, such as the spine or other part of the brain. Treatment related reaction in the brainstem may be more toxic due to a more restricted space and closer proximity to high-risk anatomic structures. The first 3 patients in each stratum will be observed at least for 6 weeks before the next set of patients are enrolled.

- If there are no RLTs in the first 3 subjects, enrollment will commence continuously within each stratum.
- If 2 or 3 RLTs occur in the first 3 subjects, accrual will be suspended and the investigator, PNOC leadership and Sponsor will make decisions regarding continuation of study accrual.
- If a RLT occurs in 1 of the first 3 patients, an additional 3 patients will be enrolled in that stratum and observed for at least 12 weeks. In this case:
 - If fewer than 2 of the first 6 patients in each stratum experience RLT with at least 12 weeks of follow-up, the remaining patients will be enrolled.
 - If a RLT occurs in ≥ 2 of the first 6 patients accrual will be suspended and the investigator, PNOC leadership and Sponsor will make decisions regarding continuation of study accrual.

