10.3 Interim Analyses and Stopping Rules

The study will be monitored by Drs. [name] and [name] and the PNOC Operation's office on a weekly basis including a review of all adverse events and deviations entered within Advarra[®] in concordance with the PNOC requirements for phase 1/2 clinical trials. The toxicity monitoring rules for the following events will be applied to all patients treated in the study. The regimen limiting toxicity (RLT) will be based on the tolerability observed following the vaccine doses following radiation therapy.

RLT includes any of the following events that occur during or following any vaccine given.

- Any grade 2 or greater autoimmune reaction.
- Any grade 3 or greater hematologic or non-hematologic toxicity with the exception of lymphopenia.
- Any life-threatening event.
- Any other unexpected Grade 2 or greater neurological deficit, which is possibly, probably, or definitely related to the vaccine therapy that does not respond within 21 days trial of 0.3mg/kg day dexamethasone or equivalent (max 12mg/day) or Avastin or equivalent (10mg/kg every 2 weeks for a maximum of 3 doses)

In addition to the stopping rules specific to the design detailed above, all patients will be monitored continuously for treatment-related adverse events by the study PIs Drs. [name] and [name].

Sequential boundaries will be used to monitor the RLT rate. The accrual will be halted if excessive numbers of RLTs are seen, that is, if the number of RLTs is equal to or exceeds b_n out of *n* patients with full follow-up (see table below). This is a Pocock-type stopping boundary that yields the probability of crossing the boundary at most 0.0475 when the rate of RLT is equal to the acceptable rate of 0.20.

For example, in Stratum A, the trial will be stopped if the number of RLTs is equal to or exceeds b_n out of *n* patients with completed follow-up.

Number of Patients, n 1 2 3 4 5 6 7 8 9 10 11 12 13 14 15 16 17 18 19

Boundary, b_n - - 34445556 6 6 7 7 7 8 8 8 9

This boundary is equivalent to testing the null hypothesis, after each patient, that the event rate is equal to 0.2, using a one-sided level 0.021430 test.

θ	φ*	E[Y]	SD[Y]	E[N]	SD[N]	E[Y/N]	SD[Y/N]
0.20	0.0475	3.70	1.62	18.51	2.39	0.21	0.13
0.30	0.2248	5.08	1.55	16.92	4.44	0.34	0.18
0.40	0.5327	5.60	1.49	14.00	5.76	0.48	0.20
0.50	0.8151	5.30	1.54	10.59	5.62	0.60	0.20

Definitions:

Y = the number of events, random, between 0 and N N = the number of patients, random, between 1 and K

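### Section 6.3 ties regimen limiting toxicity to the vaccine alone, so read literally a nivolumab-only toxicity does not block continued nivolumab in Stratum C, and the early accrual gate cites no definition

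*Combined protocol and SAP*

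**What the plan says.** **Section 6.3.** An RLT is one of four event types occurring between the first vaccine dose and 30 days after the eighth. It counts if it is among those that "are considered either possibly, probably, or definitely to the vaccine" (the word *related* is evidently missing). The condition stands ahead of the list and governs all four items. The section's opening sentence names the nivolumab combination; the attribution clause does not.

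**Section 10.3.** The same four items appear under a different lead-in: "RLT includes any of the following events that occur during or following any vaccine given". There is no end date. Only the neurological item carries an attribution, to the vaccine therapy. The section says its "toxicity monitoring rules for the following events will be applied to all patients treated in the study", and it drives a sequential boundary counted in "patients with full follow-up (see table below").

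**Accrual gate.** Section 10.1.4 says: "If there are no RLTs in the first 3 subjects, enrollment will commence continuously within each stratum". Accrual is suspended at 2 or 3 RLTs in the first 3 patients, or at 2 or more in the first 6. Section 3.5 repeats that "the first 3 patients in each stratum will be observed for RLTs for at least 6 weeks". Neither section says which RLT list applies. Section 3.5 refers the reader to Section 9.3, which covers efficacy.

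**Continuation.** Under Section 6, "stratum C patients may continue to receive nivolumab every 3 weeks after the 8th dose for a total of 96 weeks" if disease is stable or improved and therapy is tolerated. Table 6.2, footnote 2, sets the condition as a patient who "tolerates the therapy well (defined as not having any regimen related toxicities (RLT); see" Section 6.3.

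**The concern.** Safety of the vaccine with nivolumab is the only primary objective of Stratum C (Section 2.1). Two decisions in that stratum turn on the RLT count: whether accrual continues past the first 3 or 6 patients, and whether a patient goes on receiving nivolumab after dose 8.

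The protocol foresees toxicity from nivolumab itself; Section 6.4 sets out monitoring for immune-mediated myocarditis from the checkpoint inhibitor. If such an event is attributed to nivolumab and clearly not to the vaccine, Section 6.3 as worded leaves it out of the test that permits more nivolumab. At the gate, whether the same event counts depends on which section the reader opens. A numeric safety rule should not leave that to choice.

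**Working it through.** **1. The plan's own boundary figures reproduce.** An exact binomial recursion over the printed boundary (n = 3 to 19) gives crossing probabilities of 0.0475, 0.2248, 0.5327 and 0.8151 at RLT rates of 0.20, 0.30, 0.40 and 0.50. All agree with Section 10.3. The issue is which events are counted, not the arithmetic.

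**2. The two definitions side by side.**

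| | Section 6.3 | Section 10.3 |
|---|---|---|
| Start | dose 1 | any vaccine dose |
| End | 30 days after dose 8 | none stated |
| Attribution, all items | to the vaccine | none |
| Attribution, neurological item | to the vaccine therapy | to the vaccine therapy |
| Tied by citation to | continuation test | its own boundary |

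Dose 8 falls at week 21, so the Section 6.3 window is 21 + 30/7 = 25.3 weeks.

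**3. Take a grade 3 event judged due to nivolumab alone, within the window.**
- *Continuation test:* Section 6.3 is cited, its attribution clause is not met, and the event is not an RLT.
- *Boundary:* Section 10.3's grade 3 item has no attribution, so the event counts.
- *Gate:* it counts if Section 10.3 is meant and not if Section 6.3 is meant. The gate's minimum observation periods, 6 and 12 weeks, lie inside 25.3 weeks, so at those looks attribution is what separates the two readings.

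**4. Why no gate effect is quantified.** The one observed rate is 1 RLT in 29 patients without nivolumab (Section 5.1.5). Any nivolumab rate must be assumed. With r the nivolumab-caused rate and f the share called at least possibly vaccine-related:

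- counted rate p = 1 − (1 − 1/29)(1 − r·f)
- P(suspend) = P(≥2 of 3) + P(exactly 1 of 3) × P(≥1 of next 3)

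| Assumed r | f = 1 | f = 0.9 | f = 0.5 |
|---|---|---|---|
| 5% | 0.067 | 0.060 | 0.036 |
| 10% | 0.149 | 0.131 | 0.067 |
| 20% | 0.351 | 0.309 | 0.149 |

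These figures treat p as fully realised by each look. If p instead accrues uniformly over 25.3 weeks (also an assumption), r = 10% and f = 1 give p = 0.131. That is 0.131 × 6/25.3 = 0.031 by week 6 and 0.131 × 12/25.3 = 0.062 by week 12. Suspension is then 0.018 counting only new patients at the second look, or 0.027 if the first three are followed to week 18. With f = 0.9 the corresponding values are 0.016 and 0.024. The answer thus moves from about 0.15 to about 0.02–0.03 on the onset assumption alone, and the gap between f = 1 and f = 0.9 shrinks from 0.018 to about 0.003. The documents do not settle r, f or onset.

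**The case against.** **The gate may already be sound.** The reference to Section 9.3 in Section 3.5 may be a stale pointer to Section 10.3. Section 9.3.1.4 shows the same one-section slip, citing 5.2.4 for the pseudo-progression text now in 6.2.4. Section 10.3 also refers back to the design's stopping rules straight after its RLT list. If Section 10.3 governs the gate, nivolumab-only events already count in three of the four items. This is plausible and cannot be excluded, but it is inference: the text never says so.

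**Exclusion should be rare.** Section 9.6 reserves *unrelated* for events clearly not related, and grades relation to the intervention rather than to each agent. Section 1.3 expects nivolumab to amplify vaccine-triggered responses. Most immune events would be called at least possibly vaccine-related. This stands, and it is why the effect is judged small.

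**Other safeguards apply.** Continuation is permitted, not automatic, and Section 6 speaks of tolerating the combination. Section 3.3 stops treatment for unacceptable events, Section 6.4 holds it for suspected myocarditis, Appendix I governs nivolumab toxicity, and adverse events are reviewed weekly. All true, but none of these repairs the Section 6.3 clause or tells the reader which list the gate uses.

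**Stronger readings to resist.** A reader might infer that the sequential boundary is blind to nivolumab toxicity. It is not: Section 10.3's list has no general attribution. A reader might also infer a large loss of gate sensitivity, such as 0.27 falling to 0.09 for 10% vaccine plus 10% nivolumab-only toxicity. That requires every nivolumab-only event to be excluded, the whole rate to be realised by the gate looks, and Section 6.3 to govern the gate. The documents establish none of these.

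**Conclusion.** Wrong as written, of minor to moderate severity. The firm part is the continuation test: it cites Section 6.3 by number, and Section 6.3's attribution clause omits an agent that the test allows to continue to week 96. The gate part is an ambiguity, since neither Section 10.1.4 nor Section 3.5 names a definition. The practical effect is probably small, given the attribution scale and the other safeguards. No gate magnitude is claimed, because the nivolumab RLT rate, the share attributed to the vaccine and the time of onset are all unknown. The boundary's stated operating characteristics are not in question.

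**What to change.** 1. In Section 6.3, including its neurological item, and in the neurological item of Section 10.3, replace the vaccine or vaccine therapy as the object of attribution with *any study agent (K27M/TT vaccine, poly-ICLC or, in Stratum C, nivolumab)*.
2. Have Sections 10.1.4 and 3.5 cite the amended Section 6.3 for the gate, and correct the Section 9.3 reference in Section 3.5.
3. Otherwise leave the Section 10.3 boundary's events, window and patient-entry rule alone. Closing its window at 30 days after dose 8 would discard late RLTs while nivolumab continues. With a 20% rate in the window and a further 5 or 10 points later, crossing at n = 20 (extending the printed rule, b = 9) would fall from 0.12 or 0.23 to 0.048.

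**Cost.** A wording amendment. Slightly more Stratum C patients may fail the continuation test, and the gate may suspend slightly more often than under a literal Section 6.3 reading. Compared with reading Section 10.3 at the gate, events judged clearly unrelated to every study agent would no longer count there. The boundary would gain only nivolumab-attributed neurological deficits that meet the existing item and are not already counted by another.

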6.4 Suspected Myocarditis

Given the potential risk of immune-mediated myocarditis (inflammation of the heart) from check point inhibitor, patients will be evaluated by CPK and cardiac troponins from baseline and throughout treatment. Should myocarditis be suspected or as otherwise clinically indicated, treatment should be held and patient evaluated with a cardiology consult and TDI-derived strain echocardiography or cardiovascular magnetic resonance imaging should be considered.

7 Study Procedures and Observations

7.1 Schedule of Procedures and Observations

The study-specific assessments are detailed in this section and outlined in Table 6.1 and Table 6.2. Screening assessments must be performed within 14 days prior to enrollment unless otherwise noted or in the case of H3.3K27M and HLA confirmation. Treatment or visit delays for public holidays or weather conditions do not constitute a protocol violation.

A written, signed, informed consent form (ICF) and a Health Insurance Portability and Accountability Act (HIPAA) authorization must be obtained before any study-specific assessments are initiated. A copy of the signed ICF will be given to the subject, and a copy will be filed in the medical record. The original will be kept on file with the study records.

All patients who are consented will be registered in OnCore[®], the UCSF Helen Diller Family Comprehensive Cancer Center Clinical Trial Management System (CTMS) that is being used for PNOC related trials. The system is password protected and meets HIPAA requirements.

7.1.1 Eligibility Assessments

The Eligibility procedures and assessments must be completed within 14 days prior to enrollment unless otherwise noted.

Strata A & B:

- Complete medical history, including history of prior treatments and initial and/or other preradiotherapy MRIs
- Performance status
- Brain MRI; spine MRI only if clinically indicated
- Concomitant medications
- Complete blood count (CBC) with differential and platelet count
- Blood chemistry assessment, including:
 - Aspartate aminotransferase/alanine aminotransferase (ALT/AST), total bilirubin, creatinine and albumin
- Females of child-bearing potential will have a serum or urine beta-HCG pregnancy test

Stratum C:

- Complete medical history, including history of prior treatments
- Brain MRI; spine MRI only if clinically indicated
- Performance status
- Pulse oximetry
- Concomitant medications
- Complete blood count (CBC) with differential and platelet count
- Blood chemistry assessment, including:
 - Aspartate aminotransferase/alanine aminotransferase (ALT/AST), total bilirubin, creatinine, lipase, amylase, albumin, and C-reactive protein (CRP)

- TSH (if TSH is abnormal also measure free T4)
- Urine analysis (UA)
- Females of child-bearing potential will have a serum or urine beta-HCG pregnancy test.

